5.0 Study Procedures

5.1 Cognitive Training and Rehabilitation Intervention

Cognitive training and rehabilitation will be administered by a Cognitive Intervention Specialist who will be trained and supervised by [name] (Co-PI). During hospitalization, enrolled patients assigned to the intervention arm will undergo two 20-minute cognitive training sessions daily, 7 days a week. The first session will occur within 24 hours of ED presentation. If an unanticipated delay with the initial cognitive training session occurs (e.g., patient leaves for a procedure or radiographic procedure), the cognitive training will be administered as soon as feasibly possible. The Cognitive Intervention Specialist will primarily administer the cognitive training Monday through Friday from 8A to 4P. If the Cognitive Intervention Specialist is not available (e.g., weekends), then cognitive training will be administered by trained CTAs.

Table 2. Cognitive training during hospitalization

Orientation exercise
Forward and backward digit span
Memory and problem solving
Reverse digit spans
Letters-numbers
Puzzles, games, hobbies

Table 3. Key Components of Goal Management Training

I. Slip-Ups	Overall Introduction; Psychoeducation; Define Goals and Absentminded Slips; Raise Awareness of Consequences of Slips.
II. Stop the Automatic Pilot	Define Automatic Pilot and How Leads to Errors; Learn how to "STOP" Automatic Pilot.
III. The Mental Blackboard	Define the Mental Blackboard; Learn How to "STOP" and Check Mental Blackboard.
IV. State your Goals	Define Goals; Learn How to State Goals; Practice "STOP" and "STATE."
V. Making Decisions	Define Competing Goals; Learn How to Split Goals; Practice "STOP-STATE-SPLIT."
VI. Splitting Tasks into Subtasks	Define Overwhelming Goals; Learn How to Split Goals; Practice "STOP-STATE-SPLIT."
VII. Checking (STOP)	Learn How to Recognize Errors in "STOP-STATE-SPLIT" Cycle; Review How to Use "STOP" to Monitor Daily Tasks; Wrap-Up.

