Confusion Assessment Method for the Intensive Care Unit (CAM-ICU, Appendix C)	Patient	1 min	X	X		
Delirium Assessment Battery (Appendix G)	Patient	5 min	X	X		
Richmond Agitation Sedation Scale (RASS, Appendix H)	Patient	Observation	X	X		
Delirium Motor Subtyping Scale-4 (DMSS-4, Appendix I)	Patient	Observation	X	X		
Confusion Assessment Method Severity (CAM-S, Appendix J)	Patient	Observation	X	X		
Blood and urine [#]	Patient	5 min	X	X		
Demographics, education, substance abuse, sensory impairment, recent hospitalization, region of residence, highest occupation, height, weight, hospitalization in past 6-months.	Patient / Informant	5 min	X			
Quick Dementia Rating Scale (QDRS, Appendix K)	Informant	3 min	X			
Everyday Cognition (eCOG, Appendix U)	Informant	5 min	X			
Montreal Cognitive Assessment (Appendix V)	Patient	5 min	X	X ^o		X
Older American Resources and Services Activities of Daily Living Scale (OARS ADL, Appendix L)	Patient / Informant	5 min	X			X
Mini-Nutritional Assessment (Appendix M)	Patient / Informant	2 min	X			
Clinical Frailty Scale (Appendix N)	Patient	Observation	X			X
Hopkins Rehabilitation Engagement Rating Scale (Appendix E)	Patient	Observation		X*	X*	
Life Space Assessment (Appendix F)	Patient/ Informant	5 min	X			X
Repeatable Battery for the Assessment of Neuropsychological Status (RBANS, Appendix O)	Patient	30 min				X

DKEFS Proverbs (Appendix P)	Patient	4 min				X
DKEFS Color-Word Interference (Appendix Q)	Patient	3 min				X
DKEFS Category Switching (Appendix R)	Patient	3 min				X
Trails A and B (Appendix W)	Patient	5 min				X
EQ-5D-5L (Appendix S)	Patient / Informant	5 min				X
Death, nursing home placement, or rehospitalization	Patient / Informant / Medical record	2 min				X
Brain MRI	Patient	45 min				X
Propositional density	Patient writing sample [^]	None	X			

Table 4. Prospective data collection schedule. ^o MOCA to be performed at 120 hours or at hospital discharge, whichever comes first. ^{\$} hospital discharge only. ^{*}To be performed at hospital discharge and after the cognitive rehabilitation sessions are completed. #, Blood and urine will be collected at enrollment and 72 hours; 120 hour blood and urine is optional. [^]Home writing samples will be used to calculate propositional density.

“Observation” in the “Duration” column indicates that these measures are obtained by observing the patient during routine research activities.

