5.2a. Delirium will be assessed for in the ED at screening and 3-hours, and once daily throughout the hospitalization if enrolled for 10 days and at discharge, whichever comes first. Trained CTAs will perform the **modified Brief Confusion Assessment Method (bCAM, 1 minute, Appendix B)** in non-mechanically ventilated patients or the **Confusion Assessment Method for the Intensive Care Unit (CAM-ICU, Appendix C)**. The modified bCAM can be reliably performed by our non-physician research staff. It is 82% to 86% sensitive and 93 to 96% specific for delirium with a kappa of 0.87 indicating excellent interobserver reliability.⁴³ The CTAs will also perform the **Delirium Assessment Battery (Appendix G, 5 minutes)** to capture additional delirium assessments such as the CAM, 3D-CAM, and 4AT for our sensitivity analyses.⁴⁴⁻⁴⁷

5.2.b. Delirium Heterogeneity Factors

Delirium heterogeneity factors will be collected once daily in the ED and hospital to help identify delirium phenotypes using LCA (Aim #3). These heterogeneity assessments do not require any additional patient interaction and arousal, psychomotor activity, and severity can be observed while performing the delirium assessments. **Arousal** will be determined with the **Richmond Agitation Sedation Scale (RASS, Appendix H)**^{48,49} Patients will be categorized as having delirium with normal arousal (RASS = 0), decreased arousal (RASS < 0) or increased arousal (RASS > 0). **Psychomotor activity** will be assessed by using the **Delirium Motor Subtyping Scale-4 (DMSS-4, Appendix I)**.⁵⁰ This observational scale is an abbreviated version of the more complex 11-item Delirium Motor Subtyping Scale (DMSS) with very good agreement (κ = 0.63 to 0.92).^{50,51} Patients will be categorized into hypoactive, hyperactive, mixed, and no psychomotor subtype delirium. **Delirium severity** will be determined by the short form **Confusion Assessment Method Severity (CAM-S, Appendix J)** and will be categorized as none (0 points), low (1 point), moderate (2 points), or severe (3 to 7 points).⁵²

5.2.c. Establishing Pre-illness Cognition and Intelligence

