7.3. Index hospital exploratory outcomes

- Delirium duration was defined as the total # of days a patient was delirious or comatose. Delirium was measured daily using the bCAM³⁷ (non-mechanically ventilated) and CAM-ICU³⁸ (mechanically ventilated). We chose the bCAM and CAM-ICU because of their high specificity (>=95%).
- Mean delirium severity throughout hospitalization using the Confusion Assessment Method Severity (CAM-S) scale.³⁹
- Maximum delirium severity throughout hospitalization using the CAM-S
- In-hospital death
- Total number of parenteral (intravenous and intramuscular) doses benzo/antipsychotic medications given during hospitalization adjusting for days in the hospital:
- Hospital length of stay
- ICU length of stay
- Post-discharge disposition in those who survived hospitalization

8. Statistical Methods

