- 3) To account for the potential differences in survival between the intervention and usual care groups, we will treat death as the worst outcome in those who died before the 4-month follow-up and assign these patients an RBANS score of 39.
- 4) To determine how multiple imputation impacted our findings, we will do a complete case analysis of patient who had missing RBANS.

We will re-run the proportional odd logistic regression models using the same covariates as our primary analysis.

8.4. Heterogeneity of treatment effect analysis for primary outcome:

Because detecting a statistical interaction may require significantly greater statistical power than detecting a main effect, a p-value for the interaction term < 0.20 will be considered as the threshold by which effect modification is potentially present. We will evaluate effect modification of the following variables:

- 1) Age
- 2) Severity of illness as defined by APS of the APACHE II
- 3) Years of education
- 4) Enrollment delirium severity (CAM-S)
- 5) Enrollment psychomotor subtype (hypoactive, hyperactive, mixed, normal)

- 6) Enrollment level of arousal (normal, decreased, increased)
- 7) Enrollment etiology (drug, infection, metabolic/endocrine, organ dysfunction, CNS)
- 8) Time from ED presentation to randomization, which is a surrogate to time to first cognitive intervention
- 9) Hopkins Rehabilitation Engagement Rating Scale (HRERS), which is a measure of patient engagement with the cognitive intervention. Patients in the usual care arm will be assigned a score of 0.

For the heterogeneity of treatment effect analysis, we will re-run the proportional odd logistic regression models using the same covariates as our primary analysis.

8.5. Analyses for Secondary Outcomes: All secondary outcomes analyses will be intention-to-treat using the same approach as our primary outcome.

- 1) Multivariable proportional odds logistic regression will be performed for executive function composite score, MoCA, OARS ADL, and EQ-5D-5L at 4-months using the same covariates.
- 2) For 4-month mortality, multivariable logistic regression will be performed. If there are less than 30 events, only a univariate analysis will be performed.
- 3) For nursing home placement, multivariable logistic regression will be performed. If there are less than 30 events, only a univariate analysis will be performed.

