We will adjust for the same covariates as the primary analysis. However, the number of covariates incorporated will depend on the number patients and events for the proportional odds logistic regression and logistic regression models, respectively. For our proportional odds logistic regression model, we will have one degree of freedom available for every 10 to 15 patients with completed outcome measurements.⁴⁷ For our multivariable logistic regression models, we will have one degree of freedom available for every 10 to 15 outcomes for our multiple logistic regression models.⁴⁷ We will incorporate the covariates in order of importance. Proportions and medians with their IQR will be reported for the intervention and usual groups for categorical and continuous outcomes, respectively. Unadjusted and adjusted odds ratio (aOR) with their 95% confidence intervals (95%CI) will also be reported.

8.6. Analysis for Exploratory Outcomes (4-month and index hospitalization): All exploratory outcomes analyses will be intention-to-treat. For these outcomes, unadjusted comparisons using the Wilcoxon Rank-sum tests or chi-squared test will be performed for continuous and categorical variables, respectively. Unadjusted odds ratios will be reported. A p-value < 0.05 will be considered statistically significant.

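### Mean CAM-S is averaged over a stay that ends at discharge, so discharge timing alone can move it, and the plan does not say whether the pre-treatment rating counts in the mean or the maximum.

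*SAP*

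**What the plan says.** The SAP's section on index hospital exploratory outcomes (the second of two sections numbered 7.3) includes "Mean delirium severity throughout hospitalization using the Confusion Assessment Method Severity (CAM-S) scale" and "Maximum delirium severity throughout hospitalization using the CAM-S". It states no start day, end day or denominator, and no rule for the enrolment rating or for days of coma or after death.

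The ratings come from the protocol. Section 5.2.b, which covers arousal, psychomotor activity and CAM-S severity, says "Delirium heterogeneity factors will be collected once daily in the ED and hospital", and Table 4 marks CAM-S in both the ED and the hospital columns. Section 5.2a schedules the delirium assessments "once daily throughout the hospitalization if enrolled for 10 days and at discharge, whichever comes first". Patients must be delirious to enrol. In Protocol 5.1, on cognitive training, "The first session will occur within 24 hours of ED presentation", after consent and randomisation.

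For exploratory outcomes, SAP 8.6 says that "unadjusted comparisons using the Wilcoxon Rank-sum tests or chi-squared test will be performed", with p < 0.05 called significant. Hospital length of stay is another outcome in the same list, and Protocol 9.1 asks whether training reduces it. Only the count of parenteral drug doses is adjusted for days in hospital.

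**The concern.** Higher CAM-S is worse. A patient who clears and leaves contributes mainly the bad early days. A patient who clears and waits for discharge adds low-score days that pull the mean down. If the arms differ in time to discharge, the mean compares different windows of illness, and the unadjusted test has no means of separating the two. SAP 8.2 declines to adjust for post-randomisation covariates because treatment could affect them, yet dividing by the number of days in hospital brings such a quantity into the outcome.

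The second issue is the enrolment rating, which no training can influence. If it is counted, it can set a floor under each patient's maximum. These two measures are the SAP's only severity outcomes for the in-hospital part of the intervention, so a real effect on severity could be missed or misread, and an undefined window leaves the choice to the analyst.

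**Working it through.** The plan gives no effect size, SD or power for CAM-S, so there is no figure of its own to reproduce. The check uses arithmetic on daily scores, then illustrative simulation.

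**1. One course, different discharge days.** Mean = sum of ratings / number of ratings. For scores 6, 4, 2, 0, 0, 0, 0 the sum is 12 however long the patient stays beyond the first zero:
- discharged after 4 ratings: 12/4 = 3.0
- after 5: 12/5 = 2.4
- after 7: 12/7 = 1.71

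Without the first rating the sum is 6, and the means are 6/3 = 2.0, 6/4 = 1.5 and 6/6 = 1.0. Dropping the enrolment rating does not remove the dependence on stay. The maximum is 6 in all three cases.

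**2. Different speeds of recovery, discharge at the first zero.**
- 6, 3, 0: 9/3 = 3.0
- 6, 4, 2, 0: 12/4 = 3.0
- 6, 5, 4, 3, 2, 1, 0: 21/7 = 3.0

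The stay-long mean cannot tell these patients apart. Over a fixed 10 days, counting days after discharge as zero, they score 9/10 = 0.9, 12/10 = 1.2 and 21/10 = 2.1.

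**3. Simulation with fixed waits.** From the documents: 282 enrolled (SAP 8.7) at 1:2 (Protocol 4.2), hence 94 and 188; Wilcoxon test at 0.05, taken as two-sided. Assumed: enrolment CAM-S 3 to 7; noisy linear fall averaging 1.2 points a day when the arms have the same course, or 1.6 (intervention) against 1.1 (usual care) for faster recovery; discharge 0 to 3 days after recovery; at most 11 ratings; 300 runs. Entries are intervention vs usual care, with the rejection rate in brackets. The first two result columns include the enrolment rating.

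| Scenario | Stay-long mean | Maximum | Maximum, enrolment excluded | Fixed post-enrolment days |
|---|---|---|---|---|
| Same course; leave 0 vs 3 days after recovery | 2.36 vs 1.61 (100%) | 5.02 vs 5.02 (5%) | 3.87 vs 3.87 (5%) | 0.99 vs 0.99 (6%) |
| Faster recovery; both leave at recovery | 2.32 vs 2.37 (7%) | 5.03 vs 5.01 (6%) | 3.45 vs 3.98 (65%) | 0.69 vs 1.09 (100%) |
| Faster recovery; leave 0 vs 2 days after | 2.31 vs 1.83 (99.7%) | 5.01 vs 5.01 (6%) | 3.44 vs 3.97 (66%) | 0.69 vs 1.10 (99.7%) |
| Faster recovery; both leave 2 days after | 1.64 vs 1.83 (50%) | 5.00 vs 5.02 (6%) | 3.43 vs 3.98 (72%) | 0.69 vs 1.10 (99%) |

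In rows 1 and 3 the stay-long mean is significant in the wrong direction. Excluding only the enrolment rating leaves it wrong: 1.79 vs 1.17 in row 1 and 1.58 vs 1.38 in row 3. The fixed-day column uses the full simulated course, including days after discharge, which the trial would not observe.

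**4. Simulation with random waits.** Assumed: peak 3 to 7 at enrolment, linear clearing over 2 to 8 days, exponential wait averaging 3 days, 10-day cap, 200,000 per arm. With delirium 20% shorter in the intervention arm, the stay-long means are:
- same wait: 1.64 vs 1.75 (right direction)
- wait 1 day shorter: 1.76 vs 1.75 (benefit gone)
- wait 2 days shorter: 1.95 vs 1.75 (reversed; chance that a random intervention patient scores worse 0.59, against 0.50 for no difference)

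Using only ratings observed before discharge on the two days after enrolment, the comparison is 2.85 vs 3.24 in each of these scenarios. It is about 3.24 in both arms when delirium is identical.

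**The case against.** Several stronger readings are tempting, and the documents do not support them.

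- **That both outcomes include the pre-treatment rating.** The SAP does not say so. SAP 8.4 names enrolment CAM-S as a separate variable, and Table 4 has separate ED and hospital columns. Inclusion is a natural reading of a whole-stay measure, but the exact finding is that nothing excludes it.
- **That earlier discharge also makes an arm look worse on the maximum.** A shorter window can only lower a maximum or leave it unchanged. Randomisation balances the enrolment value, so its inclusion dilutes an effect without biasing it. That severity peaks at enrolment is an assumption of the simulations.
- **That a better arm should be expected to score worse.** Reversal needs a shorter wait after recovery on top of faster recovery. The protocol asks whether training shortens delirium and stay; it does not say that training shortens that wait. With equal waits the mean moves the right way, though less than it should.
- **That CAM-S ratings stop at day 10.** The limit is stated in Protocol 5.2a for delirium assessments. Section 5.2.b states none for CAM-S, although the scale is observed during those assessments.

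It is also fair to say that these are two of eight exploratory index-hospital outcomes. Delirium duration and length of stay are reported beside them, so faster clearing and earlier discharge would be visible there. Adjusting for enrolment CAM-S departs from the SAP's choice of unadjusted exploratory comparisons and is mainly a gain in precision.

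What stands is the arithmetic of the mean and the missing definition of the window. Neither is answered by other outcomes in the list.

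**Conclusion.** The point holds for the mean as a matter of definition: discharge timing changes it with no change in disease, from 3.0 to 1.71 in the worked patient. The consequence for the trial is attenuation of a true benefit, with loss or reversal possible only if the intervention also shortens the wait after recovery. For the maximum the point is conditional: if the enrolment rating counts, a real effect is diluted (5.03 vs 5.01 with it, 3.45 vs 3.98 without it, under the assumed courses). All simulated sizes rest on assumed trajectories and waits, and only their directions should be relied on. Priority is minor, because the outcomes are exploratory and neither the primary RBANS analysis nor any secondary outcome is affected.

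**What to change.** In SAP 7.3 and 8.6:

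1. Use only CAM-S ratings made after randomisation, for both the mean and the maximum.
2. Replace the stay-long mean with the mean over a fixed set of early study days (for example days 2 to 3), or with a repeated-measures model of daily CAM-S by study day. Step 1 alone does not cure the mean.
3. State how days after discharge, after death and in coma are handled.
4. Adjust both outcomes for enrolment CAM-S, which is already collected. The proportional odds model used elsewhere in the SAP would serve for the mean over fixed days and the maximum.
5. If the 10-day limit in Protocol 5.2a also applies to CAM-S, reconcile the whole-stay label with it.

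The cost is SAP wording and minor programming, with no new data. The downside is that patients discharged early contribute fewer ratings, so the fixed days should be early enough that most patients are still in hospital.

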Medical Record Variable	Description
Elixhauser comorbidity index ⁶¹	Summarizes the prognostic significance of 31 predefined comorbidities. Higher scores represent higher comorbidity.
Acute Physiology Score (APS) of the Acute Physiology and Chronic Health Evaluation (APACHE II) ⁶²	The APS is based upon the initial values of 12 routine physiologic and laboratory measurements. Higher scores indicate higher severity of illness.
ADRD documented in the medical record or prescribed an acetylcholine esterase inhibitor (galantamine, donepezil, and rivastigmine) prior to randomization.	This data will be used to help define pre-existing ADRD.
Drug Burden Index (DBI) ⁶³	Characterizes the patient's home exposure to anticholinergic and sedative medications. The DBI incorporates the principles of dose-response and maximal effect. ⁶³
Medications given in the ED and hospital	Daily benzodiazepines, opiates, and medications with anticholinergic properties given in the ED and hospital will be recorded. ⁶⁴⁻⁶⁶
Interventions received in the ED and hospital	Interventions such as physical, occupational, and speech therapies, consultations (psychiatry, geriatrics, or neurology), surgeries or procedures, and treatment for delirium etiologies will be recorded.
ED, ICU, and hospital length of stay	The length of stay in the ED, ICU, and hospital will be quantified by hours.
Hospital discharge disposition	The patient's hospital discharge disposition will be classified as discharged to home, assisted living, post-acute care facility, nursing home, or expired.

Table 5. Variables to be collected during medical record review.

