Table 1 lists the inclusion criteria for ECID randomized trial. Patients were included in the study if they were 65 years or older, hospitalized from the ED, can receive cognitive training within 24 hours of ED presentation, and are delirious. We enrolled patients who were 65 years or older, because delirium disproportionately affects older patients, and they were most likely to benefit from our research. Comatose patients were re-evaluated 1 to 2 hours later. If the coma was persistent, then they were excluded delirium cannot be assessed for in these patients. Additionally, they must be arousable for the cognitive intervention to be administered. Patients who were unable to follow simple commands prior to their acute illness were considered to have end-stage ADRD and may not benefit from our intervention. In addition, our delirium assessment has not been validated for these patients.

Inclusion Criteria	Exclusion Criteria

 • 65 years or older • Admitted through the ED • Cognitive training can be initiated within 24 hours of ED presentation • Delirious at enrollment as determined by the 4AT²² 	
 • Comatose • Not able to follow simple commands or non-verbal prior to the acute illness (end-stage pre-illness ADRD) • Resides in a nursing home • Prisoner • Receiving hospice care • Lives > 100 miles away from the enrolling sites • Non-English speaking • Previously enrolled • Deaf or blind • Intravenous drug, crack or cocaine, or methamphetamine use within the past one year, or any condition that, in the investigator’s opinion, makes them an unreliable trial patient or unlikely to complete the trial. • Psychotic disorder or suicidal gesture requiring hospitalization within the past one year • Discharged from the ED

Table 1. Inclusion and exclusion criteria for ECID randomized trial.

6. Treatment arms

Hospitalized patients with delirium were randomized in 1:2 ratio using permuted block randomization to either cognitive training and rehabilitation intervention or structured usual care defined as follows:

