7.1. Primary outcome at 4-months

The primary outcomes for ECID was global cognition at 4-months, as determined by a comprehensive neuropsychological assessment. Global cognition was assessed for using the **Repeatable Battery for the Assessment of Neuropsychological Status (RBANS)**. The RBANS is a comprehensive neuropsychological battery for the evaluation of global cognition

and has been validated in subjects with mild cognitive impairment, moderate to severe traumatic brain injuries, vascular dementias, and Alzheimer’s disease.²³⁻²⁷ In addition to providing a score for global cognition, it also provides individual scores for immediate and delayed memory, attention, visuospatial construction, and language. Scores range from 40 to 160, with higher scores indicating better cognition.

7.2. Secondary Outcomes at 4-months are listed in Table 2.

Study Assessment	Description
Executive function score	Based on the Delis–Kaplan Executive Function System (D-KEFS) Proverbs subscale (conceptual flexibility), the DKEFS Color Word Interference (inhibition), and DKEFS Verbal Fluency Category Switching subscale (monitoring). ²⁸ Scores range from 1 to 18, with higher scores indicating better executive function.
Older American Resources and Services Activities of Daily Living Scale (OARS ADL) ²⁹	Assesses functional status and is based on 7 basic and 7 instrumental activities of daily living. Scores range from 0 (completely dependent) to 28 (completely independent).
EQ-5D-5L ³⁰⁻³²	EQ-5D-5L characterizes quality of life and contains 5-dimensions (“5D”) related to everyday living: mobility, self-care, usual activities, pain/discomfort, and anxiety/depression. EQ-5D-5L index values, validated for the US population, were calculated, and higher scores represented better quality of life. ³³ An index value score of 1.0 indicates perfect quality of life, whereas a score <0.0 indicates quality of life worse than death. The EQ-5D-5L also asks patients to grade their current global health status from 0 (worst health you can imagine) to 100 (best health you can imagine).
Montreal Cognitive Assessment ³⁴	This is a brief test of global cognition based on attention and concentration, executive functions, memory, language, visuoconstructional skills, conceptual thinking, calculations, and orientation. Scores range from 0 to 30, with higher scores indicating better global cognition.
Mortality	Collected by medical record review or informant interview.

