8.7. Power and Sample Size

To estimate our sample size, we used half a standard deviation (SD) of that particular test to define the minimum clinically important difference (MCID) threshold. Based on our preliminary study,⁹ the SD for the RBANS was 12.4, and we considered a 6.0 point difference to be the MCID threshold. Based upon a two-sided alpha of 0.05 and 80% power, we will need outcome data in a total of 153 patients (51 intervention and 102 usual care) to detect a 6.0 difference in 4-month RBANS. Using a conservative death and lost-to-follow-up rate or withdrawal estimate

of 30% and 22%, respectively, we estimated that 282 patients would have to be enrolled to achieve this sample size.

References

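### Discharge disposition is compared only in hospital survivors, and the scored secondary outcomes have no rule for deaths, although both sets are labelled intention-to-treat

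*SAP*

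**What the plan says.** **Discharge disposition.** The SAP's list of index hospital exploratory outcomes (the second section numbered 7.3) defines the outcome as "Post-discharge disposition in those who survived hospitalization". In-hospital death is a separate item on the same list. SAP 8.6 then states: "All exploratory outcomes analyses will be intention-to-treat". It plans unadjusted Wilcoxon or chi-squared tests and declares significance at p < 0.05. Protocol Table 5 (medical record review) has disposition "classified as discharged to home, assisted living, post-acute care facility, nursing home, or expired".

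**Scored secondary outcomes.** For the executive composite, MoCA, OARS ADL and EQ-5D-5L, SAP 8.5 states: "All secondary outcomes analyses will be intention-to-treat using the same approach as our primary outcome". Under that approach (SAP 8.2), patients whose RBANS is completely missing are removed. No separate rule is given for deaths on these scores.

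**Death in the analysis.** SAP 8.3 item 3 gives patients who die before the 4-month visit an RBANS of 39, one point below the scale minimum. Its stated reason is that survival may differ between arms. The section is headed for the primary outcome only. SAP Table 2 says of the EQ-5D index that "a score <0.0 indicates quality of life worse than death", which places death at 0 on that scale. Mortality at 4 months is a secondary outcome with its own model.

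**The concern.** Randomisation makes the arms comparable at entry. It does not make the survivors comparable if the intervention affects who survives. An arm that keeps more frail patients alive brings them into its own average for function, quality of life and discharge destination; an arm that loses them is spared that. The SAP applies the same logic elsewhere: it declines to adjust for post-randomisation variables because treatment may affect them, and it adds the RBANS death analysis because survival may differ. Neither safeguard reaches disposition or the scored secondary outcomes.

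What is at stake is the reading of secondary and exploratory results that will carry odds ratios, confidence intervals or p-values under an intention-to-treat label. With a planning death rate of 30%, the number of patients outside each 4-month score comparison is not small.

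**Working it through.** **1. The plan's own figure.** Inputs from SAP 8.7: "two-sided alpha of 0.05 and 80% power"; "the SD for the RBANS was 12.4, and we considered a 6.0 point difference to be the MCID threshold"; allocation 1:2 (SAP 6); 30% deaths; 22% loss or withdrawal.

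- Usual-care n = 3 × (12.4 × (1.960 + 0.842) / 6)² = 100.6, so 101 + 51 = 152 by the normal approximation. An exact t-test with 51 and 102 has power 0.8005, which gives the stated 153.
- Enrolment: 51 / (0.70 × 0.78) = 93.4, so 94 intervention patients; 3 × 94 = 282, as stated.

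The 282 therefore already assumes that the dead supply no score: 0.30 × 282 = 84.6 deaths (28.2 of 94 and 56.4 of 188), leaving 282 × 0.546 = 154 with data. The RBANS analysis is planned in followed-up survivors, and the secondary scores inherit its approach.

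**2. Scored outcomes: illustration.** The documents give no arm-specific death rates, so these are assumptions. Each simulated patient has a normally distributed frailty, the frailest die, the score correlates 0.5 to 1.0 with frailty, and treatment changes nobody's score. Usual-care deaths are 30%. Analysed patients: 94 × (1 − death rate) × 0.78 = 55 to 62 intervention, and 188 × 0.70 × 0.78 = 103 usual care.

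| Intervention deaths | Survivor difference (SD) | Approximate OR | Chance of significant false harm (nominal 2.5%) |
|---|---|---|---|
| 30% | 0 | 1.00 | 2.5% |
| 25% | −0.04 to −0.10 | 0.93 to 0.82 | 4% to 9% |
| 20% | −0.08 to −0.20 | 0.87 to 0.68 | 7% to 23% |
| 15% | −0.12 to −0.30 | 0.82 to 0.59 | 11% to 45% |

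With death ranked worst, the unequal-mortality scenarios give OR 1.05 to 1.39 in favour of the intervention, because the combined ranking counts the survival gain. Swapping the arms' death rates reverses the sign of the survivor bias.

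**3. Effect of covariate adjustment.** The figures above are unadjusted. Take deaths of 33% in usual care and 24% with intervention (30% overall, since (2 × 33 + 24) / 3 = 30). Mean frailty among survivors is φ(c) / (1 − death rate), with c the frailty cut-off: 0.541 and 0.409, a gap of 0.131. Multiplying by a correlation of 0.5 or 0.8 gives a bias of −0.07 or −0.11 SD (SD of all randomised patients). Adjusting in simulation for one baseline frailty measure, correlated 0.5 to 0.9 with true frailty, leaves about −0.02 to −0.09 SD.

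**4. The same on the OARS scale.** Assume the extra survivors score 12 and the rest 20.

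- Deaths 33% v 24%: (0.67 × 20 + 0.09 × 12) / 0.76 = 19.05 against 20.0, an apparent loss of 0.95 points.
- Deaths 31% v 28%: (0.69 × 20 + 0.03 × 12) / 0.72 = 19.67 against 20.0, a loss of 0.33 points on a 28-point scale.

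**5. Disposition: illustration.** Assume 30% of all randomised usual-care patients go to a facility and every extra hospital survivor also goes to one.

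- In-hospital death 10% v 5%: facility among survivors is 0.30/0.90 = 33.3% against 0.35/0.95 = 36.8%; OR = (0.35/0.60) / (0.30/0.60) = 1.17. Yet 60% of all randomised patients go home in each arm.
- 5% v 2%: OR 1.10. 15% v 8%: OR 1.23. Equal in-hospital death: OR 1.00.

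Disposition is tested unadjusted, so adjustment gives no relief there.

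**The case against.** The strongest reply is that the SAP hides nothing. The survivor restriction is written into the disposition outcome's name, in-hospital death sits beside it, and 4-month mortality has its own model. A reader can see any survival difference. That stands as disclosure, but seeing a difference does not correct the other contrasts.

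Three stronger readings are tempting, and the documents do not support them.

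- *That the SAP dropped a level from an ordinal endpoint.* Protocol Table 5 is a data-collection list and never calls its categories ordered. The protocol's own analysis (9.1) concerns discharge to a post-acute care facility, and SAP 8.6 plans a chi-squared test for categorical outcomes.
- *That the SAP restricts the scored outcomes to survivors.* No sentence says so. The removal rule names RBANS only; its application to the other scores is inferred from the shared approach.
- *That the intervention will look worse.* The documents project no mortality effect and describe the intervention as minimal risk. Every arm-specific death rate above is an assumption, and the SAP calls its 30% conservative. Patients leaving both arms in equal proportion causes no bias.

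Planned adjustment also helps the scored outcomes. With 153 outcomes and one degree of freedom per 10 to 15 patients, 10 to 15 are available, enough to reach frailty (priority 8 in SAP Table 4) unless it is dropped for correlation with another covariate. The bias then shrinks without vanishing.

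Finally, ranking about 30% of patients as tied worst makes each score partly a mortality comparison. That is a reason to show both versions, not to omit one.

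**Conclusion.** The point holds in a limited form. For disposition, the survivor restriction is explicit and contradicts the intention-to-treat label. For the four scored secondary outcomes, exclusion of the dead follows by inference, and the SAP's own reason for the RBANS death analysis applies to them equally.

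The bias needs a survival difference, and its direction follows the arm with more deaths. In the scenarios tried it ran from 0 to about 0.30 SD unadjusted. For a 9-point mortality difference it was about 0.07 to 0.11 SD before and 0.02 to 0.09 SD after adjustment for one frailty measure. For disposition the spurious odds ratio was 1.10 to 1.23 for in-hospital death differences of 3 to 7 points. These are illustrations on assumed rates, not forecasts.

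The primary outcome already has its death-ranked analysis, so the primary conclusion does not change. This is a minor to moderate point.

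**What to change.** 1. **Disposition.** Analyse it in all randomised patients with *expired* kept as a category in the planned chi-squared test, beside the survivor-only table. Use *expired* as the worst level of an ordered analysis only if the SAP first states an ordering.
2. **Scored secondary outcomes.** Extend SAP 8.3 item 3 to them as a sensitivity analysis. Rank death below the scale minimum for OARS ADL, MoCA, the executive composite and the EQ-5D 0–100 rating. For the EQ-5D index set death at 0, the anchor implied by SAP Table 2, and note that survivors with an index below 0 then rank below death.
3. **Labels.** In SAP 8.5, describe the main secondary-score analyses as conditional on survival and follow-up rather than intention-to-treat, and say explicitly how deaths are handled.

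**Cost.** SAP wording and a re-run of models and tests already planned; deaths are already collected, and the sample size, driven by RBANS, stays as it is. The downside is that the combined results mix survival with function, so both versions must be reported together.
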